## **Overall Statistical Analysis Plan**

NIH funding will support a mixed methods study including a randomized controlled trial and qualitative research to evaluate the impact of CRx-D. This research will fill important gaps in knowledge about how to best leverage clinical care visits to identify, support and improve outcomes for ADRD caregivers and PWD. For each aim, we provide exemplary hypotheses.

Aim 1: Among ADRD caregivers who screen positive for one or more unmet HRSNs, we will evaluate the longitudinal effects of CRx-D versus usual care on caregiver self-efficacy (10 outcome) and 20 outcomes including: psychosocial (unmet needs, social isolation, well-being, burden, depression, stress), behavioral (resource use), and health and healthcare utilization. We will also examine effects of the intervention on care recipient well-being, resource needs and use, health and health care utilization (reported by caregiver as the proxy).

Hypothesis 1a. The intervention group will report higher levels of self-efficacy at 12 months compared to controls.

Hypothesis 1b. Caregivers in the intervention group and their care recipients will have fewer unmet needs and higher rates of community resource use at 12 months than controls and their care recipients.

Hypothesis 1c. Caregivers and PWD in the intervention group will have better health and well-being at 12 months than controls.

**RCT Strategy, Timeline, Methods, and Key Measures:** A consecutive sample of caregivers seeking care at UCMC will be enrolled Y1Q3-Y2. Eligible subjects will include patients who live in the target region, identify as an ADRD caregiver and agree to receive text messages from the research team (>98% of people screened for CRx-2 could receive texts). Recruitment will occur in three outpatient sites: primary care, gynecology and Senior Care – South Shore (SCSS). Researchers will consecutively approach patients in the waiting room, screen willing patients for eligibility and enroll eligible patients.

An estimated 6% of all US adults today are ADRD caregivers (and the number is growing). Two thirds of ADRD caregivers are ≥ 50 years. AA/B people are twice as likely as whites to have dementia and are more likely to be home-dwelling. Approximately 40K patients who live in target region will be seen in the 3 recruitment sites during a 12 month period (~87.5K visits/year); 60% of these patients are ≥50 years and 75% are AA/B. Given the race and age composition of the target patient population, we estimate that 6-9% of patients approached for enrollment will be ADRD caregivers.

We will need to approach between 7K-10.5K patients living in the target region to recruit 364 ADRD caregivers (344 for the RCT + 20 for pretesting). This conservative assumption derives from this calculation: 10,550 patients \* 0.06 ADRD caregiver rate \* 0.71 willing to be screened (rate from CRx-2 trial) \* 0.81 cooperate (rate from CRx-2 trial). In CRx-2, we approached 3,100 UCMC patients over 8 months (387/month) to enroll 411 people into a trial with similar burden (length and number of surveys). For this study, we will need to approach 387-583 patients/month and have staffed and budgeted accordingly. To account for unforeseen challenges in recruiting, we have allotted 24 months for enrollment. If enrollment does not meet expected targets during the first quarter, we

will expand recruitment to the ER. This site sees 32-40K patients/yr from the target region and was a successful recruitment site for CRx-1 and -2. In addition, SCSS sees more than 250 PWD/yr from the target region. We can also recruit ADRD caregivers from SCSS. In two recent ADRD caregiver studies, we easily met recruitment goals at SCSS with high cooperation rates (>90%). From this group, we will recruit a caregiver advisory board using a community-engaged research approach that we created together with community members and have applied in several prior successful studies.

Preliminary data indicate that 52% of caregivers will have ≥1 unmet HRSNs. To ensure equal numbers between groups, we will use stratified randomization to allocate subjects to usual care or CRx-D by number of unmet HRSNs (0 or ≥1). Randomization will occur immediately after enrollment using the method of permuted blocks and the uniform random number function in Stata (v15). A stratum will be closed for enrollment once its accrual goal has been reached.

(1) Usual Care Arm: the usual care arm includes typical clinic visit procedures, including, but not limited to: meeting with a Patient Service Representative, receipt of a printed after visit summary (AVS), notification of any financial obligations and scheduling any future visits as appropriate. Usual care may also include information about community resources from the patient's healthcare team.

(2) CommunityRx-Dementia (CRx-D): In this arm of the study, caregivers will receive usual care in addition to CRx-D. CRx-D will be initiated by the Community Resource Specialist (a researcher) at the baseline (index) primary care visit (academic primary care, geriatrics, ob/gyn clinics). Caregivers assigned to CRx-D and will receive: (a) a brief, structured educational intervention about common resource needs among ADRD caregivers (e.g., "It is recommended that we talk with caregivers of people with dementia about community resources that may be helpful. Many caregivers benefit from resources like support groups or respite care. It is also common for caregivers to need help with things like food or rent and utility support."); (b) delivery and review of a personalized resource "prescription" (HealtheRx-D) for vetted resources near the caregiver's preferred location to address HRSNs (e.g. food, housing, interpersonal safety and social support) and ADRD caregiver needs (e.g. ADRD education, support groups, respite care, advance care planning); (c) demonstration of use of an online Community Resource Finder that participants can use to find and share community resources (for HRSNs, caregiving and any self-care needs), give feedback and request additional resource information; and (d) coaching on how to activate community resources, including how to reach the Community Resource Specialist.

All caregivers will complete an interviewer-administered baseline survey. Those randomized to the intervention arm will complete the survey prior to receipt of the CRx-D intervention. In addition to the printed "HealtheRx-D" delivered at the time of the baseline visit, the HealtheRx will be texted to the participant and, if the participant wishes, emailed within 24 hours of the baseline visit. The initial encounter will be followed by a series of timed text messages from the Community Resource Specialist offering ongoing community resource linkage support. At any time, a participant can reply "stop" to stop receiving text messages from the CRx-D Community Resource Specialist. Table 2 describes the frequency and content of automated text messages that will be sent to caregivers randomized to CRx-D. The CRx-D Community Resource Specialist, [name], is trained in NowPow's system and will use its "nudge" technology to send tracked text messages at

the intervals outlined below. The content of these messages is based on a text messaging experiment conducted during the CMMI HCIA CRx study. The timing of these messages is informed by the Critical Time Intervention model. Participants will be informed at the time of enrollment and in text message communications that the Community Resource Specialist will respond to text messages within 24 hours during regular work days and within 48 hours of weekends or holidays. For all participants, phone numbers will be verified via text message at the time of 7 day, 30 day, 90 day and 12 month surveys and via text message each month in between follow-up surveys. We will collect a back-up phone, mailing address and email contacts for participants (this contact info is typically documented in the electronic medical record). To maximize retention, a brief check-in will be conducted at 180 days.

The baseline survey will be administered following randomization by a trained interviewer. All caregivers will receive usual care. Participants will be blinded to the arm to which they are randomized. For caregivers randomized to the intervention arm, CRx-D will be delivered by the interviewer. Follow-up phone surveys will be conducted using computer-assisted personal interviewing (CAPI) at 7, 30, 90 days and 12 months post-enrollment. To maximize retention, a brief check-in will be conducted at 180 days and we will use text messaging and phone calls monthly between surveys to verify contact information and to schedule and remind participants about upcoming surveys. Intervention group participants can also text, email or call the CRx-D resource specialist for resource support throughout the follow-up period.

We will conduct two waves of baseline and 1 week follow-up pre-testing (Y1Q3), each with 5 ADRD caregivers with 1 or more unmet HRSNs and 5 ADRD caregivers with 0 unmet HRSNs (20 total with the two waves) to ensure survey quality and minimize risk of measurement and CAPI error. Table 1 summarizes example measures, sources and planned time points for collection. Dynamic factors will be assessed at appropriate intervals (e.g., during the last 30 days or in the interval since the last survey).

The primary outcome for Aim 1 will be assessed using the 4-item self-efficacy sub-domain from the 2015 Caregiver Dementia Care and Self-Efficacy Survey developed by Jennings et al (NIA-5P30AG028748, CMS-1C1-12-0001). We selected this relatively new measure because it is, to our knowledge, the only available measure validated specifically for ADRD caregivers that assesses self-efficacy for accessing services.

Per Jennings' protocol, responses to each of the 4 items in the self-efficacy domain will be scored from 1 to 5 (1=strongly disagree to 5=strongly agree) and averaged. We will also assess caregiver self-efficacy for self-care using our measure from the CRx-2 trial. This measure derives from Bandura's Self-Efficacy theory: "How confident are you in your ability to find resources in your community that help you manage your [your care recipient's] health?" (5-point Likert scale "not at all confident" to "completely confident"). The pragmatic CRx-2 intervention was delivered, via the routine workflow, to adult patients by clinic staff or a nurse at discharge from an outpatient visit with no specific counseling. The proposed CRx-D intervention is more intensive (e.g. delivered by the research team with a brief education component, ongoing support, caregiver access to the Community Resource Finder). We therefore hypothesize that CRx-D may also promote general self-efficacy (a broader concept than Jennings' and the CRx-2 measure) and will explore this hypothesis by administering the Generalized Self-Efficacy Scale (range 10-40) at baseline and at follow-up.

Secondary and exploratory outcomes will also be measured longitudinally. These outcomes include:

**Psychosocial Outcomes** HRSNs will be assessed at baseline and follow-up using the CMS tool. The "core" tool includes 10 validated items to assess 5 needs domains: food, housing, interpersonal safety, transportation, and utility support. We will also include the domains "family and community support" (2 items) and "financial strain" (1 item). Each domain will be scored per CMS instructions. For follow-up surveys after 1 week, we will assess needs occurring in the interval since the last interview and, when a need is identified, during the past 30 days specifically. In addition to assessing unmet HRSNs, we will assess unmet caregiving-specific resource needs, using a tool we created from prior studies and our own qualitative work.

Caregiver well-being will be assessed using PROMIS Neuro-QoL ShortForm v1.0 – Positive Affect and Well-Being. Well-being of the PWD will be assessed by caregiver proxy using the Alzheimer's Disease Related Quality of Life (ADRQL) measure. Caregiver burden will be assessed using the Dementia Caregiver Burden Scale, a validated measure created by Peipert et al. Depression will be assessed using the CES-D, the most widely used measure of depression in research, and perceived stress will be assessed using the validated and widely used Perceived Stress Scale. Activation is a domain of interest for our exploratory work. We will measure caregiver activation for self-care using the validated Patient Activation Measure. We will also measure caregiver activation for PWD's care using the validated Managing Your Loved One's Health (MYLOH) measure developed by consultant [name] and colleagues.

**Behavioral Outcomes** As the field and related technology advance, "closed loop" data documenting community resource use will emerge. These data require that both the referring institution (e.g. the primary care clinic) and the receiving organization (e.g. ADRD support group) are using the same technology platform. If closed loop data become available, we will use those. For now, we plan to assess self-reported resource use (by the caregiver and by the care recipient by proxy) using items developed for CRx-1 and 2 to measure contacting, going to and sharing information about resources. Resource use will also be assessed using qualitative data from text messages between the Community Resource Specialist and the caregiver. Data generated by caregivers' use of the web-based Community Resource Finder will be used to assess resource searches, selection and sharing as well as unfulfilled requests (searches that resulted in no available resources). Text message data and Community Resource Finder data will be collected via use of the NowPow system and transferred regularly to the research team.

**Health and Healthcare Outcomes** Caregiver physical health will be assessed using the Medical Outcomes Study SF-12 and EMR data. Physical health of the PWD will be assessed by proxy using a single item global measure of physical health. Healthcare utilization will be assessed using the DEXCOM, a self-report tool developed by Co-PI [name] et al and used in CRx-2. We will explore outcomes such as days to, number and duration of ER/hospital visits, and patterns of 911 and ambulance use to test the hypothesis that supporting caregivers with community resources is associated with less need for emergency healthcare services.

**Analysis and Sample Size Justification:** To determine the impact of CRx-D on the highest risk group, Aim 1 analyses will focus on 172 caregivers with at least 1 HRSN. Descriptive statistics will be used to summarize, overall and by study arm, sociodemographic characteristics and primary

and secondary outcomes at each measured time point. The mean, standard deviation, median, and inter-quartile range will be generated for continuous variables; frequency counts and percentages will be generated for categorical variables.

The main analyses will follow the principle of intent-to-treat, and include all 172 ADRD caregivers with at least 1 unmet HRSN in the study arm to which they were allocated. We aim to minimize missing data by employing interviewer-administered surveys and communicating to participants the protections of a certificate of confidentiality. Using these strategies, item non-response ranged from 0-3% in the CRx-2 trial. To avoid potential bias due to missing data, analyses will be conducted using multiple imputation with the chained equations method or inverse probability weighting to account for dropout and/or item non-response. In addition, characteristics of caregivers who complete each follow-up survey will be compared to caregivers who do not.

To fully leverage the longitudinal data, generalized linear mixed-effects models (GLMM) will be fit with particular interest in the time (7, 30, 90 days and 12 months post-enrollment) by study arm interaction; baseline values will be included as a covariate. Based on this model, appropriate contrasts to test the intervention effect at specific time points (e.g., 12 months) will be constructed. These contrasts will permit examination of early versus late intervention effects, valuable information for future iterations of this and other ADRD caregiver self- and family management interventions. GLMM can be used for continuous (e.g., mean caregiver self-efficacy for providing care score, patient satisfaction score, stigma score), ordinal (e.g., physical health of PWD by proxy) or binary (e.g., resource use, resource sharing) outcomes. Models will include covariates moderately associated with the outcome to remove differences attributable to baseline covariates and increase precision of the estimate of the treatment affect. Latent growth curve modeling is a viable alternative to GLMM and will be explored when sufficient variability in the distributions of patterns of outcomes by time points exist (e.g., with the binary outcomes there will be a limited number of potential patterns).

Potential moderators of the intervention effect (e.g., race, sex) will also be assessed by inclusion of a moderator by study arm interaction term. Although in the CRx-2 trial we saw no gender differences in outcomes, special consideration will be given to sex (as measured by self-reported gender) as a biological variable (moderator) and variation in intervention effects will be examined in accordance with NIH policy. In addition, based on preliminary evidence of similarity across race and ethnic groups from the CRx-2 trial, we hypothesize that the intervention effect will be similar and will analyze for dramatic departures from this outcome (e.g., whether the intervention has no or negative effect among non-Hispanic white caregivers versus a strong positive effect among AA/B caregivers) through effect modification analyses such as testing of the race by intervention interaction. Also, we will use mediation analyses to identify factors that mediate the relationship between the study arm and the outcome of interest. Improved understanding of moderating and mediating factors will facilitate future improvements to the intervention. For example, if the relationship between intervention effect and caregiver burden at time t is mediated by self-efficacy at time t-1, as posited in our conceptual framework, future improvements might focus the intervention's messaging more explicitly on fostering caregiver self-efficacy.

Transition models will be used to further study the impact of CRx-D on state changes in other outcomes, including unmet needs, well-being and resource use. This model will be of the general

form: logit P(Yit = 1 | Yit-1 = yit-1) = X + yit-1 + yit-1\*X where X is the intervention group variable and Yit is a binary outcome variable for subject i at time t. This approach will allow us to determine the frequency of transitioning into and out of a state (e.g., having any unmet HRSNs to having no unmet HRSNs) and how the intervention impacts on these transitions. This model can be extended to permit ordinal outcomes (e.g., self-efficacy for finding services to help care for the PWD). We will assume a first-order Markov model but check the sensitivity of the model to this assumption and will use robust standard errors.

We will also use survival analysis methods and methods for analyzing count data (e.g., Poisson or negative binomial regression) to explore acute and emergency healthcare utilization. For example, time from enrollment to first home EMS or ER visit will be calculated for each subject and those who never have one of these events will be censored at the end of study follow-up. Stratified Cox proportional hazards regression models will be fit with intervention group as the independent variable and clinical enrollment site as a stratification factor, due to the potential for different underlying rates based on clinical site. The proportional hazards assumption will be checked using log-log plots of survival and Schoenfeld residuals.

For the primary outcome (self-efficacy for providing care at 12 months) a sample of 86 caregivers/arm allows for detection of an intervention group difference of 0.43 points (sample size calculation using a group allocation of 1:1; power=0.8;  $\alpha$ =0.05, mean=2.8 and SD=1). With this sample size, power is sufficient to see at least a half a standard deviation (SD) difference in caregiver self-efficacy between intervention and control groups; half a standard deviation is considered a minimally important difference. Assuming 25% attrition, we will still be able to detect a difference equal to half an SD. Attrition in the pragmatic CRx-2 trial was 20%; this was an even lower-intensity intervention with no ongoing resource support nor touchpoints between follow-up surveys. In higher-intensity caregiver support studies, attrition rates range from 4% (MIND Study at 18 months) to 10% (REACH-II Study at 6 months). We will follow all caregivers through 12 months even if they no longer care for the PWD.

**Aim 2.** Among all ADRD caregivers (those who do and do not screen positive for unmet HRSNs), evaluate acceptability of the intervention as well as the effects of CRx-D plus usual care versus usual care alone on the health care experience, including satisfaction with care (10 outcome), experiences of stigma during clinical care and likelihood of sharing community resource information with others.

Hypothesis 2a. Among intervention group participants, the CRx-D intervention will be acceptable to caregivers with and without unmet HRSNs.

Hypothesis 2b. There will be no evidence, comparing the intervention group to controls, that CRx-D decreases caregiver satisfaction with care or promotes caregiver stigma.

Hypothesis 2c. Among ADRD caregivers with no unmet HRSNs at baseline, those randomized to the CRx-D intervention will demonstrate a lower likelihood of developing an unmet HRSN. In addition, they will exhibit a higher likelihood of sharing resource information with others compared to those randomized to usual care.

**Strategy, Timeline, Methods, and Key Measures:** Aim 2 will utilize RCT data (collected as described in Aim 1) from ADRD caregivers with and without unmet HRSNs. For Aim 2, the primary outcome of interest is satisfaction with care. Satisfaction will be assessed 7 days post-discharge from the caregiver's primary care visit using the Patient Satisfaction Questionnaire 18-item short form (PSQ-18). The PSQ-18 is widely used in research and shows internal consistency with the long form of the PSQ, an 80-item survey developed in 1976. The 18 items are grouped into 7 domains; each domain is scored separately (there is no overall score). The general satisfaction sub-scale of the PSQ (2/18 questions) is the most relevant PSQ domain for our study.

To assess stigma, we will use the Discrimination in Medical Settings Scale (DMS). The DMS was adapted from the Everyday Discrimination Scale for medical settings and has been tested for reliability and validity among African Americans. It includes 7 items, each scored on a 1 to 5 scale to generate a mean overall score.

Using the same transition model approach described for Aim 1, we will study the impact of the intervention on state changes in unmet needs specifically among caregivers without unmet needs at baseline. This approach will fill a gap in knowledge about the joint incidence of unmet HRSNs and ADRD caregiving needs over time.

Lastly, among those assigned to the intervention group, we will examine caregivers' propensity for sharing information about resources, comparing a) those with and without unmet HRSNs at baseline and b) among those without baseline unmet HRSNs, by study arm. Based on Maslow's Theory of Human Motivation, we hypothesize higher caregiving self-efficacy and well-being rates at 12 months among caregivers who shared resource information with others and that the effect will be highest for caregivers with unmet baseline HRSNs.

**Analysis and Sample Size Justification** Physician concern about negatively impacting patient satisfaction or causing stigma are barriers to intervening to address unmet needs. To address these, we hypothesize that satisfaction with care will not be significantly diminished among caregivers randomized to CRx-D compared to those randomized to usual care. Aim 2 analyses will include all caregivers enrolled in the trial (N=344).

We will use the analytic approach described for Aim 1. Here, we discuss analytic issues unique to Aim 2. To facilitate ease of interpretation of the primary outcome, we will linearly rescale the composite score for the PSQ-18 subdomain of general satisfaction (questions 3 and 17). Five possible responses for each of the two items are scored 1 to 5; with a higher score equating to higher satisfaction. Scores will be transformed using the formula: y= 100 \* (x-a)/(b-a) where y=the transformed score, x=the original score, a=the minimum possible score and b=the maximum possible score. Transformed items will be averaged to generate the composite score (range 0-100). Of particular interest for the non-inferiority hypothesis (H2b) will be the confidence interval for the difference (usual care - CRx-D) and whether or not the upper limit of the confidence interval exceeds the non-inferiority margin. Of note, superiority of the intervention with respect to stigma, unmet needs and other outcomes will also be tested as this can be done without penalty. Caregiver satisfaction will be measured at 7 days following the baseline outpatient visit; no longitudinal analyses will be conducted for this outcome. Typically, analyses of patient satisfaction data adjust for case-mix (age, education and general health status); this will be feasible, but given the randomized design and single-site analysis, adjustment should not be necessary. In addition,

to determine whether there are substantial differences in the intervention's effect on ADRD caregivers with unmet HRSNs compared to ADRD caregivers without unmet HRSNs, the intervention by unmet HRSNs interaction will be tested. As in Aim 1, we will examine for differential intervention effects on primary and secondary outcomes among racial and ethnic groups, and by sex, using effect modification analyses. Some analyses will be restricted to the group without HRSNs (N=172) to provide a more complete assessment of the impact of the intervention on this group (e.g., incidence of unmet HRSNs over time).

The proposed sample size of 344 is sufficient based on a non-inferiority margin of 7.6 points in patient satisfaction (primary outcome) assuming group allocation 1:1, power=0.8, one-sided  $\alpha$ =0.025, standard deviation=25. The non-inferiority margin of 7.6 points is less than half of the standard deviation for mean transformed general satisfaction scores in a population-based sample (e.g., male [mean=65, SD=23], female [mean=64, SD=24]); half a standard deviation is considered a minimally important difference.

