The first step in the proposed program of research is to pretest the single-blind, randomized controlled trial procedures and administration of the intervention and data collection procedures to inform the design of a larger randomized controlled trial (RCT). Given the pause of in-person medical visits and shelter-in-place orders due to the COVID-19 pandemic, we will pretest remote recruitment and consent procedures as well as remote intervention delivery. Interviewers will administer telephone or video-based surveys; self-administration of a web-based follow-up survey will also be offered. We will enroll up to 404 caregivers of people with ADRD, (both with and without unmet health-related social needs (HRSNs),10 caregivers enrolled in the remote pretest, 344 caregivers in the RCT for a 12-month follow-up, and an additional 50 male caregivers in the RCT for a 3-month follow-up. All human subjects will be consecutively screened for inclusion and enrolled

as described in Section P. Recruiting Methods. Following screening, participants will be screened for unmet HRSNs and then randomly assigned to either usual care or usual care plus CommunityRx-Caregiver. Usual care is described below in Section G. Use of Controls or Placebos.

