A Globus endpoint will be created by the Biological Sciences Division's Information Services pointing to the [name] file share on PRFS. The endpoint will be configured to force encryption of the data channel. A dedicated subdirectory within the file share will be created, and a guest collection will be created permitting authorized users to access that subdirectory. NowPow will be granted access to that collection, and will use Globus (either the client or API) to transfer files into the dedicated subdirectory where they may be retrieved by an analyst in the [name] Lab.

G. Experimental controls and use of placebos

Caregivers in this study will be randomized to either usual care or usual care plus the CommunityRx-Caregiver intervention.

The usual care study arm for caregivers who are patients includes typical clinic visit procedures, including, but not limited to: meeting with a Patient Service Representative, receipt of a printed after visit summary (AVS), notification of any financial obligations and scheduling any future visits as appropriate. Usual care may also include information about community resources from the patient's healthcare team.

Usual care for caregivers who are not patients but accompany a person with dementia for their care may experience procedures and information similar to those described above.

H. Type and number of experimental subjects

Individuals will be contacted for enrollment using methods described below in Section P. Recruiting Methods. Individuals will be contacted, screened for inclusion, recruited for study participation and participate in the informed consent process. Following enrollment, caregivers will be assessed for HRSNs using the CMS Accountable Health Communities tool and stratified by HRSNs (no HRSN vs. \geq 1 HRSN) and randomized to either usual care or usual care plus the CommunityRx-Caregiver (CRx-C) intervention. We will enroll up to 404 caregivers, (10 caregivers enrolled in the remote pretest, 344 caregivers in the 12-month RCT (follow-up for 120months), and an additional 50 male caregivers in the 3-month RCT (follow-up for a 3-month follow-up).

Inclusion criteria:

- Resides in the target geographic region of the study
- Self-identifies as a caregiver of a home-dwelling person with Alzheimer's disease or other related dementia using an adaptation of the Behavioral Risk Factor Surveillance Survey caregiver module

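### The SAP places the interviewer-administered baseline survey, which supplies the baseline self-efficacy covariate, after randomization; finishing it before allocation is released would protect the primary analysis at almost no cost

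*SAP*

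**What the plan says.** The order is set out in the Overall Statistical Analysis Plan, Aim 1, under RCT Strategy, Timeline, Methods, and Key Measures. On allocation it says: "Randomization will occur immediately after enrollment using the method of permuted blocks". On the survey it says: "The baseline survey will be administered following randomization by a trained interviewer". On delivery, in the same paragraph, it says: "For caregivers randomized to the intervention arm, CRx-D will be delivered by the interviewer".

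The self-efficacy score is the mean of four items, each scored 1 to 5. It is the Aim 1 primary outcome. The Overall SAP analysis section and the Aim 1 SAP (Analysis Plan) both enter the baseline value as a covariate in the longitudinal mixed model that yields the 12-month contrast.

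The documents also state some protections:

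- Blinding: "Participants will be blinded to the arm to which they are randomized". The final protocol, Section C, likewise plans to "pretest the single-blind, randomized controlled trial procedures".
- Sequence: "Those randomized to the intervention arm will complete the survey prior to receipt of the CRx-D intervention".

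The final protocol puts only the HRSN screen ahead of assignment. Section C has it that "participants will be screened for unmet HRSNs and then randomly assigned to either usual care or usual care plus CommunityRx-Caregiver", and Section H says: "Following enrollment, caregivers will be assessed for HRSNs using the CMS Accountable Health Communities tool and stratified by HRSNs". Section C keeps the baseline survey interviewer-administered (by phone, video or online) but does not say whether the rest of it falls before or after allocation.

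**The concern.** Adjusting for a baseline measurement is safe when allocation cannot have influenced it. Here the survey follows allocation and is given by a person in the role that also delivers the intervention. The stated protections deal with the participant's knowledge of the arm and with exposure to CRx-D before the survey. They do not deal with an interviewer who knows the arm while asking the questions. No text withholds allocation from the interviewer until the survey is complete.

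If that knowledge changed how answers were prompted, clarified or recorded, and did so differently by arm, part of the shift would pass through the covariate into the adjusted 12-month contrast. An upward shift in the intervention arm would understate the effect; a downward shift would overstate it.

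Stratification needs only the HRSN screen before allocation, so nothing stated in the design requires the survey to come second.

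**Working it through.** **1. The plan's own figure.** Inputs from the Aim 1 sample size text: 86 per arm, SD 1, power 0.8, alpha 0.05 (sidedness not stated), difference 0.43.

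- The normal approximation, two-sided, gives 85 per arm for 0.43. A one-sided test would need only 67, so the plan's calculation is two-sided.
- The two-sample t calculation at 86 per arm gives a detectable difference of 0.430, which reproduces the stated figure.
- With 25% attrition, 0.75 × 86 = 64.5 per arm, and the detectable difference is 0.497. This agrees with the plan's claim of half an SD.

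None of these depends on when the survey is taken relative to allocation.

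**2. How a shifted baseline enters the estimate.** Let s be the difference between arms in recorded baseline that is caused by knowledge of the arm, and b the within-arm slope of the outcome on baseline. In a baseline-adjusted comparison at one time point (a simplification of the longitudinal model):

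bias ≈ −b × s

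A simulation check with 4,000 trials per setting, 86 per arm, true effect 0.43 and b = 0.5 gave a mean estimate of 0.431 with s = 0 and 0.383 with s = +0.1. The change is −0.048, against −0.5 × 0.1 = −0.05 from the formula.

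**3. A plausible size for s.** The documents give neither b nor s, so both are assumptions.

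- A one-step change on one of four items moves the mean by 1/4 = 0.25.
- A shift of 0.1 therefore needs 0.1/0.25 = 40% of one arm, about 34 of 86 people, to move one step on one item. That is already large for blinded respondents answering fixed-response items.
- A shift of 0.3 would need 0.3/0.25 = 1.2 steps from every person in one arm, so shifts that large are not used here.

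| Assumed slope b | s = 0 | s = 0.1 |
|---|---|---|
| 0.3 | 0 | 0.03 |
| 0.5 | 0 | 0.05 |
| 0.7 | 0 | 0.07 |

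Entries are absolute bias in points. The largest is 0.07/0.5 = 14% of the minimally important difference (half an SD, 0.5 points).

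**4. Whether the planned baseline table would reveal it.** Assume the planning SD of 1 also applies at baseline.

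- SE of the difference between arms = √(2/86) = 0.1525.
- 95% half-width = 1.96 × 0.1525 = 0.30.
- For s = 0.1, z = 0.1/0.1525 = 0.66, and the chance of two-sided p < 0.05 is about 10%.

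A shift of this size would usually look like chance imbalance, so the by-arm summary is a weak diagnostic.

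**The case against.** There are four serious points on the other side.

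- **Who handles allocation is unclear.** The SAP's own description of the CRx-D arm, and Section C of the final protocol, have the Community Resource Specialist initiate the intervention. The interviewer may therefore have had no need of the allocation. This stands as a reason not to presume unblinding. It does not remove the gap: the SAP also says the interviewer delivers CRx-D, one person could hold both roles, and neither description conceals the arm during the survey.
- **The order sits in text about an in-person workflow.** That text describes waiting-room recruitment and a printed resource list, whereas the final protocol moved to remote consent and scheduled surveys and does not repeat the order. This lowers confidence that the order was followed in practice. The protocol does not contradict or replace it, however.
- **The harm is conditional and modest.** It needs the interviewer to know the arm and to influence fixed-response answers from blinded participants, differently by arm. This is accepted. Zero is compatible with the documents, and the upper end of the illustration is 0.07 points.
- **Much of the fix may come too late.** The SAP reports in the past tense that data were analyzed. For those participants only disclosure is possible. That limits the remedy but does not make the disclosure worthless: if allocation was concealed until the survey was complete, one sentence saying so closes the question.

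**Conclusion.** The concern holds, as an inexpensive improvement to a stated design choice rather than a demonstrated bias. The SAP specifies allocation first and the interviewer-administered baseline second, uses that baseline in the primary model, and does not conceal the arm from the interviewer in between.

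The illustrative bias is 0 to 0.07 points in either direction, or 0 to 14% of the minimally important difference. That range rests on an assumed slope of 0.3 to 0.7 and an assumed differential shift of no more than 0.1 points. Confidence is medium, because the documents do not say when interviewers learned the arm. Since the planned baseline summary is unlikely to expose a shift of this size, prevention is better than later diagnosis.

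**What to change.** **Any further enrollment.** Revise the two sentences in the Overall SAP (Aim 1, RCT Strategy) on the timing of randomization and of the baseline survey. The HRSN screen and the full baseline survey should be completed and locked before allocation is generated or released to the interviewer. State also whether the interviewer or the Community Resource Specialist delivers CRx-D, so that the two descriptions agree.

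**Participants already enrolled.** State when allocation was released and to whom, and read the by-arm baseline self-efficacy summary in that light. A model without the baseline score is optional, since it cannot by itself separate bias from chance imbalance.

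**Cost.** A change in form order and two sentences of text, or one statement of fact for past participants. No added staff, visits or models are needed. The 86 per arm, the 0.43-point detectable difference and the baseline adjustment all stay. The one trade-off is that caregivers who stop partway through the survey would not be randomized, so slightly more may need to be consented; the documents give no rate for this. In return, no randomized participant would lack the covariate for that reason.
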